Study Protocol and Statistical Analysis Plan

Study Title: SKIPPING with PAX: An Integrated Gross Motor and Social-Emotional Skill Intervention

Clinical Trial Identifier: NCT04656990

Date of the Document: July 30, 2019

SPECIFIC AIMS

The specific aims for the study include:

Aim 1: Evaluate the preliminary impact of the integrated intervention on social-emotional, behavioral, and gross motor outcomes at post-intervention (9 months after baseline).

H1: Children in the intervention condition will show significant improvements for the social-emotional, behavioral, and gross motor variables in comparison with children in the “usual classroom” control condition.

Aim 2: Evaluate the sustained impact of the integrated intervention on social-emotional, behavioral, and gross motor outcomes at three-month follow-up.

H2: Compared with the control group, the intervention group will show greater positive impact at three-month follow-up for social-emotional, behavioral, and gross motor outcomes, controlling for baseline levels.

Aim 3 (Exploratory): Explore whether baseline cognitive skills moderate intervention effects on post- and follow-up assessment of social-emotional, behavioral, and gross motor outcomes.

BACKGROUND AND SIGNIFICANCE

Early childhood is an especially critical time for intervention to prevent modifiable risk factors such as social-emotional, behavioral, gross motor, and related difficulties from contributing to the development of more serious problems over the lifespan. Important targets include social-emotional-behavioral adjustment (e.g., interactions with others, seeking out teacher assistance, management of emotions, staying on task, behaving well in class and on the playground) and gross motor development (e.g., running, catching, jumping, and throwing), which collectively contribute to reduced risk for adverse behavioral-health, physical health, and life outcomes in adolescence and beyond. Developmental difficulties in the social-emotional, behavioral, and gross motor domains occur in all communities but can be exacerbated for children residing in predominately low-SES communities. The need for early preventive interventions to foster healthy development is amplified in calls for research to address gaps about how to effectively intervene with children experiencing lower-SES conditions and disproportionately facing health challenges. The proposed project will help to address this gap by testing whether an integrated health intervention is effective in improving social-emotional, behavioral, and gross motor outcomes for children in early childhood.

RESEARCH DESIGN, METHODS AND DATA ANALYSIS

A total of 20 preschool classrooms were randomly assigned to either the integrated intervention condition (n=10) or the control condition (n=10). Measurement took place at the level of individual children and occurred at baseline, at the end of the intervention period (i.e., 9 months after baseline), and at three-month follow-up (i.e., 12 months after baseline).

Study Population and Recruitment. The study took place in a semi-rural community in South Carolina that is in relative proximity to a metropolitan area. South Carolina provides public preschool support for Title 1 schools through the Child Development Education Program in districts across the state—of which the Early Childhood Center is a prime example. Children attending these preschool classes are four years old at time of entry, from families with an annual income of no greater than 185% of the federal poverty level. Consequently, the study sample included preschoolers residing in low socio-economic households, with 70% of the

children qualify for free or reduced lunch. For data collection, all children in the 20 preschool classrooms were eligible for inclusion in the research sample. Parental consent was obtained to permit the child assessments.

Intervention. The intervention summarized below consisted of two components, a classroom program called PAX Good Behavior Game (PAX GBG) and a gross motor skills program called Successful Kinesthetic Instruction for Preschoolers (SKIP).

PAX GBG. Teachers first implement the GBG for a 10-minute period three days per week and then gradually increase the frequency to three 10-minute periods per day five days a week throughout the school year. Best practices for the PAX GBG indicated that while there is individual variation, teachers on average played the GBG 152 times over the school year (averaging 1488 minutes/year), with more positive outcomes in classrooms where the game is played more often.

PAX-GBG teachers participated in an orientation meeting to get an overview of the program and materials. Then, they completed a one-day online training regimen followed by two 90-minute follow-up meetings with project staff before classes began. After the program started, project staff met individually with each teacher for a brief (15 minute) check-in 3-4 times per month to support implementation and troubleshoot issues. Teachers received continuing education credit (CEUs) for their time and effort in training and mastering the PAX GBG.

SKIP. This gross motor skills training intervention is delivered on the playground by project staff to all children in the intervention classrooms. SKIP adopts an approach that teaches gross motor skills in a manner which promotes health-enhancing bouts of physical activity while fostering motivation related to social-emotional development. Children received SKIP two times per week, for 30 minutes per session, throughout the school year.

Intervention Integrity. Research staff periodically observed intervention classrooms to document implementation fidelity for the PAX GBG. SKIP intervention sessions on the playground were digitally recorded to permit observational coding of lesson plan fidelity from the videos. Data from PAX GBG and SKIP fidelity checks were used early and throughout the intervention period to take corrective action when there were indications of slippage in intervention integrity (e.g., additional support, prompts/reminders, follow-up checks). In addition to the fidelity checks, classes of children in both the intervention and control conditions were observed periodically on the playground by research team staff. The purpose of playground/recess observation was two-fold: (1) to make sure children in the intervention condition were not receiving extra training in gross motor skills during recess periods when SKIP was not being conducted, and (2) to verify that children in the control condition were not receiving gross motor skills training that mimics SKIP.

Outcomes. The outcome measures and putative moderator measures are summarized below.

Outcome Measures. The outcome measures were collected at the three assessment time points: baseline, post-intervention period, and follow-up. The outcome measures for this study focused on gross motor skills and social-emotional skills—all considered primary outcomes. At each time point, teachers completed the Social Skills Improvement System—Rating Scales (SSIS-RS). Gross motor skills were assessed using a staff-administered Test of Gross Motor

Development-3 (TGMD-3). The testing tasks were digitally recorded and then scored by trained coders who were blinded to condition and time point. The secondary outcomes were physical activity behaviors as assessed by GT3X+ accelerometers. If possible, accelerometry data were to be captured during the school day, with logs kept to denote on and off times, and all data were to be uploaded into ActiLife Software. However, because this study was a pilot RCT rather than a fully implemented RCT, there was a distinct possibility that it would not be feasible to collect the accelerometry data.

Putative Moderators. Three putative moderators were measured at baseline using executive-function cognitive-skills tasks from the NIH Toolbox. Attention and inhibitory control were assessed with the Flanker Task, cognitive flexibility with the Dimensional Change Card Sort Task, and working memory with the List Sorting Working Memory Task.

Demographic Data. Child's date of birth, gender, and ethnicity were acquired through school records.

Analytic Method for Aims 1 and 2. The preliminary step in the analytic plan was to examine the range and frequency distributions for all outcome variables, to transform variables, when necessary, to examine the zero-order correlations among baseline variables, and to confirm baseline equivalence for intervention and control groups. The analytic multi-level model used three-level hierarchical linear modeling (HLM), which involves time points (level 1: baseline, post, follow-up) nested within children (level 2) who are nested within classroom (level 3), to test intervention effects on each of the three outcome variables (social-emotional skills, problem behavior, and gross motor skills). Intervention condition was represented as a dummy variable (1 = intervention, 0 = control. Additional supplemental analyses were conducted for each of the outcome variables to explore whether intervention effects vary as a function of child sex.

Analytic Method for Aim 3 (exploratory). Aim 3 explored whether baseline executive-function cognitive skills moderate intervention effects on post- and follow-up assessment of social-emotional, behavioral, and gross motor outcomes. Exploratory moderator analysis was conducted by adding the putative moderators and their interactions with intervention condition and time to the overall analytic model. A separate model was estimated for each of the three putative cognitive-skills moderators.

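### Is the verdict on H1 and H2 left open because no alpha or claim rule is stated and problem behavior is not named as primary?

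*Combined protocol and SAP*

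**What the plan says.** Under Specific Aims, H1 predicts that "Children in the intervention condition will show significant improvements for the social-emotional, behavioral, and gross motor variables" relative to control. H2 predicts that "the intervention group will show greater positive impact at three-month follow-up for social-emotional, behavioral, and gross motor outcomes". Both hypotheses join the three domains with *and*. Neither gives a level of significance.

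Outcome Measures states that the measures "focused on gross motor skills and social-emotional skills—all considered primary outcomes". It then adds: "The secondary outcomes were physical activity behaviors as assessed by GT3X+ accelerometers". Problem behavior appears by name in neither sentence. Background and Significance treats the behavioral domain as part of a wider construct: "Important targets include social-emotional-behavioral adjustment".

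Analytic Method for Aims 1 and 2 specifies a three-level hierarchical linear model to "test intervention effects on each of the three outcome variables (social-emotional skills, problem behavior, and gross motor skills"). No multiplicity method is given there or elsewhere. Aim 1 is worded as an evaluation of preliminary impact, and Outcome Measures calls the study a pilot RCT.

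**The concern.** H1 uses the language of significance but sets no threshold. The text could be read as requiring success on all three variables or as giving a separate verdict for each. A lenient reader might even accept one success. If the reading is picked after the data are seen, the same results could be presented as support for the integrated intervention or as lack of it.

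A mixed result is quite possible. The intervention "consisted of two components, a classroom program called PAX Good Behavior Game (PAX GBG) and a gross motor skills program", and one component could work without the other.

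The silence on problem behavior adds to this. A joint rule over the two domains named as primary is easier to meet than one over the three variables tested. What would be at stake is a gain in one domain being reported as success of the whole programme.

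**Working it through.** **No figure to reproduce.** The documents state no alpha, power, effect size or correlation among outcomes. All of these are assumptions below. The only design input is the allocation: "A total of 20 preschool classrooms were randomly assigned to either the integrated intervention condition (n=10) or the control condition (n=10"). That gives 10 + 10 − 2 = 18 degrees of freedom for a comparison of classroom means.

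**Any one against all three.** Let each of three post-intervention tests have power p. If the tests are independent:

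- P(at least one) = 1 − (1 − p)³ = 1 − 0.2³ = 0.992 at p = 0.8
- P(all three) = p³ = 0.8³ = 0.512
- Disagreement = 0.992 − 0.512 = 0.480

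For equally correlated normal test statistics with correlation ρ and δ = Φ⁻¹(p):

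- P(all three) = ∫ φ(u) Φ[(δ + √ρ·u)/√(1−ρ)]³ du
- P(none) = ∫ φ(u) Φ[−(δ + √ρ·u)/√(1−ρ)]³ du

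| Assumed power | Assumed ρ | At least one | All three | Disagree |
|---|---|---|---|---|
| 80% | 0 | 99.2% | 51.2% | 48.0% |
| 80% | 0.5 | 95.0% | 61.1% | 33.9% |
| 80% | 0.7 | 92.0% | 65.9% | 26.1% |
| 80% | 0.9 | 87.2% | 72.2% | 15.0% |
| 90% | 0 | 99.9% | 72.9% | 27.0% |
| 50% | 0 | 87.5% | 12.5% | 75.0% |

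Simulated classroom means with 18-df t tests give nearly the same at 80% power: 47.9% at outcome correlation 0 and 27.2% at 0.7. The disagreement therefore runs from 15% to 75% depending on inputs that the documents do not supply. It also measures the distance to an any-one rule, which no section proposes.

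**The two readings that the text supports.** Three tests, each significant or not, give 2³ = 8 patterns. An any-one rule and an all-three rule part company in the six patterns with one or two successes. In each of those six, a per-variable report says which variables succeeded, and a joint report says that H1 was not supported in full. These statements are compatible. Both come from the same three models, and neither alters an estimate, standard error or p-value.

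**Status of problem behavior.** Setting the places side by side:

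- Specific Aims lists the behavioral domain beside the other two in Aims 1, 2 and 3 and in both hypotheses.
- Background and Significance folds it into one construct with the social-emotional domain.
- Outcome Measures limits the secondary tier to physical activity.
- Analytic Method for Aims 1 and 2 tests problem behavior on equal footing with the other two variables.

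Primary is the reading that fits all four. The status matters most if a joint rule applies, both other variables have 80% power and problem behavior has exactly no effect. With independent tests and a 0.025 chance of a false improvement, a two-variable joint rule then succeeds with probability 0.8² = 0.64 and a three-variable rule with 0.64 × 0.025 = 0.016. At outcome correlation 0.7 the simulated values are 71% and 2.5%. That contrast needs every one of those conditions, and also needs the natural reading of the status to fail.

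**False positives.** With no effect anywhere and an assumed two-sided 0.05 per test, the chance of at least one false improvement over three independent post tests is 1 − 0.975³ = 7.3%, or 5.5% at correlation 0.7 (normal approximation). Counting either direction it is 1 − 0.95³ = 14.3%. Each variable's own test stays at its nominal level. The plan claims no familywise rate, so none is broken.

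**The case for a change.** The strongest case for acting is that the gap is real and cheap to close. A level, a list of primary variables with their scores and a sentence on how H1 and H2 are judged would need no new data and no refitting. Pilot status lowers the stakes but does not supply a rule, and a mixed result is easy to imagine.

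The factual part stands: alpha, sidedness and a claim rule are absent, and problem behavior is not listed by name as primary or secondary. The arithmetic also stands under its assumptions.

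The inference to a defect does not. The large disagreement figures depend on a rule that is foreign to the plan. Writing the missing sentence would leave per-variable error rates as they are and would not control familywise error. A Holm adjustment could, but at the strictest step, 0.05/3 with 18 degrees of freedom, it would cut 80% power to about 63%, a poor trade in a pilot with 20 classrooms. The document is also written largely in the past tense. If results were already known, a rule added now would have to be labelled post hoc and would give no protection against choosing it in hindsight.

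**Conclusion.** The concern does not call for a change. The plan omits detail that analysts fill in a standard way: a conventional level, one model per outcome, and all three outcomes reported at both time points, which makes 3 × 2 = 6 estimates. Followed as written, it yields a valid result for each variable, and no sample size, stopping decision or stated error rate depends on a joint verdict.

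The disagreement of 48% (independent tests), or about 26-27% (correlation 0.7), rests on an assumed 80% power, and it describes an any-one rule that the plan does not contain. Between the readings that the text does support, the numerical difference is nil and only the summary label changes. This conclusion assumes that problem behavior is reported alongside the other two variables, as the analysis section already requires. A report that presented one favorable domain as support for the whole hypothesis would depart from the plan's own wording.

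### Should the teacher-rated SSIS-RS be analysed without baseline control because PAX teachers probably gave the baseline ratings after training?

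*Combined protocol and SAP*

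**What the plan says.** - **Rater.** Outcome Measures: "At each time point, teachers completed the Social Skills Improvement System—Rating Scales (SSIS-RS"). Blinding is described only for the TGMD-3, whose recordings were "scored by trained coders who were blinded to condition and time point".
- **Training.** Intervention, PAX GBG: after an orientation, teachers had a "one-day online training regimen followed by two 90-minute follow-up meetings with project staff before classes began". They then deliver the game themselves, so they know their condition.
- **Children.** Study Population and Recruitment: "Children attending these preschool classes are four years old at time of entry".
- **Hypothesis.** Specific Aims, H2, compares the arms at three-month follow-up on "social-emotional, behavioral, and gross motor outcomes, controlling for baseline levels".
- **Model.** Analytic Method for Aims 1 and 2 has "time points (level 1: baseline, post, follow-up) nested within children (level 2) who are nested within classroom (level 3"), with a 1/0 dummy for condition. A preliminary step is "to confirm baseline equivalence for intervention and control groups". The condition-by-time term is not written out there. The Aim 3 section adds moderators and their interactions with condition and time to the overall model.

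The documents do not date the baseline SSIS-RS relative to allocation or training, and they do not say whether the same teacher rates a child at 12 months.

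**The concern.** A class teacher can hardly rate newly entering four-year-olds before teaching them, so the baseline SSIS-RS in the PAX arm was probably given after training and with condition known. For the rater, it may then not be a pre-treatment score.

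Baseline also appears in two roles: something controlled for in H2, and an outcome row in the model. For a score with a built-in rater shift these are not equivalent. Covariate adjustment assumes that a baseline difference between arms is chance and will partly regress. A rater shift that persists does not regress, so part of it would be read as an intervention effect. An equivalence check on the SSIS-RS would likewise mix differences between raters with differences between children.

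Social-emotional skills are a primary outcome, and problem behavior presumably comes from the same form. Two of the three modelled outcomes could therefore be affected, while the blinded TGMD-3 would not.

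**Working it through.** The documents give no SD, ICC, class size, correlation or power figure, so there is nothing of the plan's own to reproduce. Only the 10 classrooms per arm comes from the text.

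**Assumed inputs.** Class size m = 10, 15 or 20; ICC = 0.05, 0.10 or 0.20; baseline-to-later correlation r = 0.4 to 0.7; regression slope equal to r; 18 df (critical value 2.101).

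**1. Bias.** Let d0 and d2 be the rating shift in the PAX arm at baseline and at the later time.
- Baseline as covariate: d2 - r × d0.
- Unconstrained condition-by-time: d2 - d0.
- Later time only, no SSIS-RS baseline: d2.

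With d0 = 0.30 SD and no true effect:

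| Later shift d2 | Covariate, r = 0.5 | Covariate, r = 0.7 | Covariate, r = 0.8 | Condition-by-time |
|---|---|---|---|---|
| 0.30 (constant) | 0.15 | 0.09 | 0.06 | 0 |
| 0.45 (grows, same rater) | 0.30 | 0.24 | 0.21 | 0.15 |
| 0 (gone, e.g. new rater) | -0.15 | -0.21 | -0.24 | -0.30 |

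A simulation with 20 classrooms, 15 children each and ICC 0.15 agreed. With a constant shift, the covariate analysis gave 0.155, 0.095 and 0.060 SD, and condition-by-time gave 0.002, 0.002 and -0.001.

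**2. Standard errors.** For a comparison at one time point, s = sqrt(2(1 + (m-1) × ICC) / (10m)), which runs from 0.140 (m = 20, ICC 0.05) to 0.237 (m = 10, ICC 0.20). Multiply s by sqrt(1 - r²) for covariate adjustment, by sqrt(2(1-r)) for condition-by-time, and by 1 for the later time only. At r = 0.6 these are 0.112-0.189, 0.125-0.212 and 0.140-0.237.

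**3. False rejection, two-sided 5%, noncentral t.**
- Constant 0.3 SD shift: covariate 8.0-26.5% over r = 0.4 to 0.7; condition-by-time 5%.
- Constant 0.1 SD shift: covariate 5-7%.
- Constant 0.3 SD shift with r = 0.8 or 0.9: residue 0.06 or 0.03 SD, rejection 6-10%.
- Shift of 0.3 SD at baseline only, r = 0.6: condition-by-time 26.9-62.3%, covariate 14.7-33.2%. At r = 0.3, plausible if a different teacher rates: 17-41% and 7-10%.

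**4. Price of giving up baseline adjustment.**
- Condition-by-time against covariate: sqrt(2(1-r)/(1-r²)) = 1.195, 1.155, 1.118, 1.085 for r = 0.4, 0.5, 0.6, 0.7, so 9-20% more.
- Later time only against covariate: 1/sqrt(1-r²) = 1.091 at r = 0.4 and 1.400 at r = 0.7, so 9-40% more.
- Power for a true 0.4 SD effect at r = 0.6, no shift: covariate 52-92%, condition-by-time 43-86%, later time only 36-77%.

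**5. Which analysis is planned?** H2 states a hypothesis and names no covariate. The methods text puts baseline among the level-1 time points. The Aim 3 wording suggests that condition and time are already in the overall model, and H1 is about improvement. Read together, these point to a condition-by-time contrast.

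**The case for a change.** The strongest case for a change is that it costs only analysis text and protects primary outcomes. A post-training baseline is the natural reading; the plan never names the contrast that tests H2; and a constant 0.3 SD shift could raise false rejection of an adjusted test to about a quarter. If raters were 0.3 SD stricter throughout, adjusted power for a true 0.4 SD effect at r = 0.6 would fall from 52-92% to 29-66%. The adjusted result could still be shown as a sensitivity analysis.

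The bias formulas stand, and so does the point that H2's wording and the model are not expressly reconciled. Three things do not carry over into a required change:

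- **H2 need not mean a covariate.** The claim that H2 as worded is biased depends on that reading, which no passage states. A model that forced equal baseline means would behave like covariate adjustment, but no such constraint is written either.
- **The same rater is not enough.** Cancellation needs a shift of the same size at both times. A teacher who delivers the programme for a school year may shift further, and that growth remains in both analyses.
- **A rater-dependent rule has its own cost.** If a new teacher rates at 12 months, condition-by-time is the more biased contrast, and the comparison without an SSIS-RS baseline is unbiased only by giving up precision. It also leaves chance imbalance between classrooms unadjusted, with SD 0.14-0.24, similar in size to the supposed shift.

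Describing the SSIS-RS results as unblinded teacher ratings is fair reporting, but it alters no analysis. Reading the lower confidence limit as the smallest shift that would remove significance restates an interval.

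**Conclusion.** No change to the plan follows. The weakness is real in principle: unblinded teachers who deliver the programme also rate two of the three outcomes. The choice between baseline as covariate and baseline as outcome affects only the part of a rating shift that was already there at baseline and stays constant. For an assumed 0.3 SD shift, covariate control would leave 0.09-0.18 SD at r = 0.4 to 0.7, and 0.03-0.06 SD at r = 0.9 to 0.8.

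The planned model already carries baseline as an outcome, so its natural contrast removes that part. The unwritten condition-by-time term is a gap that an analyst fills sensibly. Going further would exchange a certain loss of precision, 9-20% or 9-40% in the standard error with 10 classrooms per arm, for protection against a shift the documents do not show, under a rule whose direction depends on an unstated 12-month rater. For a pilot that seeks preliminary impact, leaving this as it stands is a fair trade-off.

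The sizes rest on assumed shifts, correlations, ICCs and class sizes. The post-training timing of the baseline rating is likely but inferred.

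### Ten classrooms per arm cannot confirm baseline equivalence; describe baseline instead, and pre-specify age and sex in the Aim 1 and 2 models (minor)

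*Combined protocol and SAP*

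**What the plan says.** Under Research Design, Methods and Data Analysis: "A total of 20 preschool classrooms were randomly assigned", ten to each arm. No stratification or matching is described.

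Under Analytic Method for Aims 1 and 2, the preliminary data checks end with a step "to confirm baseline equivalence for intervention and control groups". The plan names no variables, method, margin or level of analysis for this step, and no action if the arms differ.

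The main model is a hierarchical linear model of "time points (level 1: baseline, post, follow-up) nested within children (level 2) who are nested within classroom (level 3"). Its one named predictor is arm: "Intervention condition was represented as a dummy variable (1 = intervention, 0 = control"). The baseline outcome is thus one of the modelled time points, and H2 in Specific Aims speaks of "social-emotional, behavioral, and gross motor outcomes, controlling for baseline levels".

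Under Demographic Data, each child's "date of birth, gender, and ethnicity were acquired through school records". Three executive-function scores are also measured at baseline. In the analysis text, sex appears only in supplemental effect-modification analyses and executive function only in the exploratory Aim 3 models. Age and ethnicity appear in no model.

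**The concern.** Confirming equivalence is a strong claim. It needs a margin and enough precision to place the difference inside it. Ten clusters per arm give little precision on any variable that clusters by classroom, so failing to see a difference says little about whether one exists.

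Two things are at stake. A report could state that the arms were shown to be equivalent when the data cannot carry that statement. And because no action is attached to the check, an apparent imbalance would leave any covariate adjustment to be chosen after seeing the data, while an imbalance that escapes notice would go unadjusted. A short covariate list fixed in advance avoids both, and the plan already collects two obvious candidates, age and sex.

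**Working it through.** The documents give no figure to reproduce: there is no ICC, class size, margin, alpha or power.

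**Inputs.** From the plan: 10 classrooms per arm, hence 20 − 2 = 18 degrees of freedom. Assumed: m = 10, 15 or 20 assessed children per classroom; ICC 0.05, 0.10 or 0.20; child-level SD of 1; two-sided alpha 0.05; equivalence margin ±0.25 SD.

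**Formulas.**
- SE of the baseline arm difference = sqrt[(2/10) × (ICC + (1 − ICC)/m)]
- 95% chance range under randomisation = ±1.96 × SE
- Smallest difference flagged = t(18, 0.975) × SE = 2.101 × SE
- Room for showing equivalence by two one-sided 5% tests = 0.25 − 1.734 × SE; a negative value means that even an observed difference of zero would fail at the expected SE

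**One case in full** (m = 15, ICC 0.10): SE = sqrt[0.2 × (0.10 + 0.90/15)] = sqrt(0.032) = 0.179. Chance range ±0.35. Flag threshold 2.101 × 0.179 = 0.38. Equivalence room 0.25 − 1.734 × 0.179 = −0.06. Power to detect a true 0.25 SD difference (noncentral t) is 0.26.

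| m | ICC | SE | 95% range ± | flagged above | power at 0.25 SD | equivalence room |
|---|---|---|---|---|---|---|
| 10 | 0.05 | 0.170 | 0.33 | 0.36 | 0.284 | −0.045 |
| 10 | 0.10 | 0.195 | 0.38 | 0.41 | 0.228 | −0.088 |
| 10 | 0.20 | 0.237 | 0.46 | 0.50 | 0.169 | −0.160 |
| 15 | 0.05 | 0.151 | 0.30 | 0.32 | 0.349 | −0.011 |
| 15 | 0.10 | 0.179 | 0.35 | 0.38 | 0.262 | −0.060 |
| 15 | 0.20 | 0.225 | 0.44 | 0.47 | 0.182 | −0.140 |
| 20 | 0.05 | 0.140 | 0.27 | 0.29 | 0.395 | 0.008 |
| 20 | 0.10 | 0.170 | 0.33 | 0.36 | 0.284 | −0.045 |
| 20 | 0.20 | 0.219 | 0.43 | 0.46 | 0.190 | −0.130 |

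The flag threshold runs from 0.29 to 0.50 SD, and there is any room for equivalence in only one scenario of nine. The SE is estimated in practice, so success is rare rather than impossible. By simulation, the power to show equivalence when the true difference is zero is about 1% at m = 15 and ICC 0.10. It is at most 32% over a wider grid (m = 8 to 20, ICC 0.02 to 0.20).

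**What leaving out a covariate costs.** The shift in the effect estimate, given a chance imbalance, is the covariate's coefficient beyond the baseline outcome times the imbalance. For 0.25 SD and assumed coefficients of 0.1, 0.2 and 0.3, this is 0.025, 0.05 and 0.075 SD.

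**What adjustment gains.** If the covariates explain a further share R² of outcome variance at both child and classroom level, the SE is multiplied by sqrt(1 − R²). For assumed R² of 3%, 5% and 10% the factor is 0.985, 0.975 and 0.949, a cut of about 1.5%, 2.5% and 5%. In classrooms this is 20/(1 − R²) − 20 = 0.6, 1.1 and 2.2. Simulated trials of 10 v 10 classrooms, adding one covariate to a model with the baseline outcome, cut the variance by 0.4–2%, 4–10% and 10–22% for coefficients of 0.1, 0.2 and 0.3.

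**The case against.** A reader might infer that the equivalence check is the plan's only guard against imbalance, or that all prognostic baseline data are left out. The documents do not support that. The baseline outcome, normally the strongest predictor, is a time point in the model, and H2 controls for baseline levels. The documents also never call age, sex or executive function prognostic; executive function is presented as a possible moderator.

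A reader might also infer that the plan tests baseline differences and treats a non-significant result as proof. No test is named. The clause may be loose wording for a routine look at the data. This stands, but the criticism does not need a test: at the assumed clustering, hardly any method would confirm equivalence within 0.25 SD.

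Nor do the omitted covariates bias the result. Under randomisation the estimate is unbiased on average; what remains is precision, and error conditional on the imbalance that happened. In a contrast of change over time, a covariate with the same effect at every visit cancels, so only its effect on change matters. This stands, and it is why the covariates must interact with time.

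The assumed ICCs may be too high for age and sex, since nothing suggests they cluster by classroom. At ICC 0 the same formula gives SE 0.10 to 0.14, flag thresholds of 0.21 to 0.30 SD and positive equivalence room of 0.005 to 0.077 SD. The strongest statement about equivalence therefore applies to class-clustered variables. Even at ICC 0 a null comparison is not itself a demonstration of equivalence.

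Finally, this is a pilot with preliminary aims, and the gain is modest. That argues for low severity. It does not argue against a change that costs almost nothing.

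**Conclusion.** The point holds in a limited form, and it is minor. Arms of 10 classrooms each cannot confirm baseline equivalence on class-clustered variables: with 10 to 20 children per class and ICC 0.05 to 0.20, only differences above 0.29 to 0.50 SD would be flagged, and a true 0.25 SD difference would be detected with about 17% to 40% power. The check should support no claim of equivalence and should not decide adjustment.

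Age and sex are collected and are absent from the Aim 1 and 2 models. Including them would bring an SE reduction of about 1.5% to 5% (if they explain 3% to 10% of variance beyond the baseline outcome, and less if they act only within classrooms). It would also guard against a conditional error of about 0.025 to 0.075 SD for a 0.25 SD imbalance. Class size, ICC, margin, coefficients and R² are all assumed.

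**What to change.** 1. Replace the equivalence clause with: *Baseline characteristics will be described by arm with standardised differences, without significance tests and without a claim of equivalence.*
2. Add: *Whatever imbalance is seen, every Aim 1 and Aim 2 model will include child age at baseline and child sex, each with its interaction with time. The model without these terms will be reported as a sensitivity analysis.*
3. Keep the executive-function scores for Aim 3, or use them only in a sensitivity analysis. Aim 3 builds a separate model per score by adding it to the main model, so a composite already in that model would bring each score in twice.

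The cost is a change of wording; both variables come from school records already obtained, and two child-level covariates make little demand on the 18 classroom-level degrees of freedom. The document describes the analyses in the past tense. If outcomes have already been analysed, label the covariate model post hoc; the equivalence wording can be corrected either way.
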